12.2 Secondary Efficacy Assessment

12.2.1 Combined Assessment of Function and Survival Score

The CAFS score will be calculated by the Sponsor to compare individual subjects to all other subjects using ALSFRS-R and date of death event as described in Table 1.

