17 STATISTICAL METHODS AND PLANNED ANALYSES

This section provides the basis for the SAP for the study. The SAP may be revised during the study to accommodate amendments to the clinical study protocol and to make changes to adapt to unexpected issues in study execution and data that may affect the planned analyses. Any deviations from the planned analysis will be described and justified in a separate document and in the clinical study report (CSR).

The following analyses related to the objectives will be done twice:

Interim Data Lock and Interim Analysis will take place when the 190th subject randomized in Study MT-1186-A02 completes the last visit in that study. At this timepoint, data-lock will combine data collected up to the Week 48 visit in Study MT-1186-A02 with data collected from Study MT-1186-A04. The timing of Study MT-1186-A04 data lock will take place at an appropriate time following completion of the MT-1186-A02 data lock.

The results will not be disclosed to any site-facing personnel or to any personnel directly involved with the conduct of the study.

Final Data Lock and Final Analysis will take place when the last subject completes the Week 50 visit or the safety follow up period of Study MT-1186-A04.

The database locks will be done for each of the above time points, respectively. Each database lock will be associated with a designated SAP that will describe Interim and Final analyses, respectively. Each SAP will be approved and signed prior to the corresponding database lock. Additional analysis may be performed if deemed necessary.

The analysis undertaken for Study MT-1186-A04 will include data from the beginning (baseline) of Study MT-1186-A02 until the end of Study MT-1186-A04. The data will also include information for subjects who early terminated during Study MT-1186-A02 or decided not to continue into Study MT-1186-A04. Further details of which visits in Study MT-1186-A02 will be analyzed for each endpoint will be described in the SAP.

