17.4.5.4 Efficacy Analyses for Secondary Endpoints

CAFS analysis ranks clinical outcomes on the basis of survival time and change in the ALSFRS-R score will be analyzed at all visits from baseline in Study MT-1186-A02 to the end of Study MT-1186-A04. In this analysis, a subject's score will be calculated by comparing each subject to every other subject within each treatment group in the study, resulting in a score of +1 if the outcome was better than the subject being compared, -1 if worse, and 0 if the same. The subject's score will then be calculated by summing up their comparison to all of the other subjects within each treatment group in the study as CAFS score. A subject who dies earlier than the comparator subject will be given a comparison score of -1. For a subject who discontinues early for a reason other than death, that subject and the comparator's score will be based on the change from baseline of the ALSFRS-R score at the latest timepoint at which they both have an ALSFRS-R score. In general, these comparisons will result in subjects who die being assigned the worst scores and ranked according to the time of death. Subjects who survive and complete the study will be ranked more favorably than subjects who die. The CAFS score will be evaluated at all visits from

baseline in Study MT-1186-A02 to the end of Study MT-1186-A04 using an ANCOVA model with treatment group and Study MT-1186-A02 randomization strata as fixed effects, and baseline ALSFRS-R total score as covariate. The difference between the 2 treatment groups in the CAFS scores will be also compared using the generalized Gehan-Wilcoxon test as a sensitivity analysis.

The following sequence of parametric and semi-parametric models will be conducted to estimate the clinical benefit:

- Mixed-effect model for repeated measure (MMRM) as specified below.
- COX PH model as specified above.

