2. INTRODUCTION

This statistical analysis plan (SAP) is based on the final global protocol (v3.0) dated 29-JUL-2022. The plan covers statistical analysis, tabulations and listings of the study data to evaluate and compare the efficacy, safety and tolerability of oral edaravone 105 mg administered once daily to Oral edaravone 105 mg administered in cycles of 'on/off' in subjects with ALS over 48 weeks in the current MT-1186-A04 study combined with 48 weeks from the MT-1186-A02 which is the parent study. The structure and content of this SAP provides sufficient details to meet the requirements identified by the FDA and International Conference on Harmonization of Technical Requirements for Registration of Pharmaceuticals for Human Use (ICH): E9 Guidance on Statistical Principles in Clinical Trials. All work planned and reported for this SAP will follow internationally accepted guidelines, published by the American Statistical Association, and the Royal Statistical Society, for statistical practice.

¹ 14 days, followed by placebo for 14 days and subsequently, repeat oral edaravone 105 mg administered for 10 days followed by placebo for 18 days

Mitsubishi Tanabe Pharma America, Inc.

The following documents were reviewed in preparation of this SAP:

- Clinical Study Protocol MT-1186-A04 Version 3.0 issued on, 29-JUL-2022
- Clinical Study protocol MT-1186-A02 Version 5.0 issued on 22-SEP-2022
- Case report forms (CRFs) for MT-1186-A02 and MT-1186-A04
- Standard Operating Procedure (SOP) GLB-BST-SOP002 for Statistical Analysis
 Plan
- ICH E9 Guidance on Statistical Principles for Clinical Trials.
- ICH E3 Structure and Content of Clinical Study Reports (CSRs)
- ICH E14 (may, 2005) clinical evaluation of QT/QTC interval prolongation

Any statistical analysis details described in this document supersede the description of statistical analysis in the protocol. In case of major differences, e.g. changes in the analysis related to the primary endpoint, a protocol amendment will be considered. The SAP may be updated during the study conduct and will be finalized before final database lock. Any deviations from the planned analysis will be described and justified in the CSR.

Mitsubishi Tanabe Pharma America, Inc.

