In case the event of at least 12-point decrease in total ALSFRS-R score or death was observed, a censor variable will be created with value 0 and 1 otherwise.

8.3.2.2. Combined Assessment of Function and Survival (CAFS) score CAFS Scoring:

CAFS analysis ranks clinical outcomes on the basis of survival time and change in the ALSFRS-R score from baseline in Study MT-1186-A02 to all post baseline visits from MT-1186-A02 until the end of Study MT-1186-A04.

To calculate a patient's CAFS score, each patient is compared individually to all other patients in the study. The summary score for each patient is the sum of the comparisons (1, 0, 1) against all other patients (Figure 2). For each pairwise comparison of patients, the patient who fares better earns a point, and the one who fares worse loses a point. In the case of a tie, no points are added or subtracted. If both participants die, the one surviving longer fared better; if only one survives then that patient fared better; and if both participants survive, the one with the smaller decline in ALSFRS-R from baseline to week 48 fared better. If a participant discontinues early or ALSFRS-R data at week 48 are missing, the participant will be treated as alive at week 48 and the ALSFRS-R at week 48 will be imputed missing using multiple imputation under missing at random (MAR).

CAFS Ranking:

Next, patients' summary scores are ranked (

Mitsubishi Tanabe Pharma America, Inc.

Figure 3).

In general, the ranking has the following characteristics:

- (1) The first patient who dies will have the lowest score and is ranked the lowest;
- (2) the last to die is ranked above all others who die;
- (3) Among survivors, the patient with the greatest decline in ALSFRS-R is ranked just above the last patient who died;
- (4) The surviving patients with the least decline in ALSFRS-R is ranked highest;

[figure not shown]
The average rank score is then calculated for each treatment group. A higher mean rank score indicates that participants in that treatment group, on average, fared better.

Figure 2:

Mitsubishi Tanabe Pharma America, Inc.

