11. CHANGE FROM THE PROTOCOL

The FAS flag definition will be changed from "all randomized subjects who received at least 1 dose of study medication and had any efficacy data collected after randomization" to "all randomized subjects who received at least 1 dose of study medication" because all randomized subjects who randomized and received at least 1 dose of study medication should be analyzed regardless of post baseline efficacy data in order to estimate treatment effect properly.

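### SAP 8.3.2.2 scores early discontinuers as alive in CAFS, with no exception for a death recorded later; this differs from the protocol and is not listed in section 11, though the effect is small

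*SAP*

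**What the plan says.** SAP 8.3.2.2 scores CAFS by pairs: "each patient is compared individually to all other patients in the study". A survivor beats a death, the later of two deaths beats the earlier, and two survivors are compared on ALSFRS-R decline. For incomplete follow-up it adds: "If a participant discontinues early or ALSFRS-R data at week 48 are missing, the participant will be treated as alive at week 48", with the missing ALSFRS-R multiply imputed under missing at random (MAR). On ranking it says: "Among survivors, the patient with the greatest decline in ALSFRS-R is ranked just above the last patient who died".

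Protocol 17.4.5.4 handles a subject who leaves early for a reason other than death differently. The pair is scored "based on the change from baseline of the ALSFRS-R score at the latest timepoint at which they both have an ALSFRS-R score". The protocol states the ranking above deaths for subjects who both survive and complete.

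SAP section 2 settles precedence: "Any statistical analysis details described in this document supersede the description of statistical analysis in the protocol". SAP section 11 has one entry, which begins "The FAS flag definition will be changed from" and concerns only the full analysis set.

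SAP 9.2.2.1.1 analyses CAFS at Weeks 24, 48, 72 and 96. The visible scoring rule names Week 48 only, and the steps that follow in 9.2.2.1.1 are not visible in the public text.

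Comparison across all subjects is not in dispute. Protocol 12.2.1 also says CAFS will "compare individual subjects to all other subjects using ALSFRS-R and date of death event".

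**The concern.** CAFS is built to rank death below survival. The alive rule is triggered by early discontinuation or a missing ALSFRS-R and carries no exception for vital status. Two kinds of subject are caught.

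- **Death recorded after discontinuation.** Protocol 9.6 and 12.2.2 and SAP 8.3.2.2.3 require phone follow-up for events after a subject leaves. A death found that way belongs to someone who discontinued early, so the literal rule scores that person as alive.
- **Vital status unknown.** Loss to follow-up is a listed withdrawal reason in Protocol 9.6. Such a subject outranks everyone with a recorded death. SAP 8.3.2.2.3 instead right-censors a subject without an observed event at the last observed date.

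Discontinuation may be related to prognosis: Protocol 9.6 withdraws subjects for tracheostomy, permanent ventilation or exacerbation of the disease. If one arm has more missing data, that arm gains ranks. The reader of the SAP is also not told that the protocol's rule has been replaced.

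**Working it through.** The plan states no power or precision figure for CAFS, so there is none to reproduce.

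**1. The rules on single pairs (assumed data).**
- A is lost after Week 12 with change -10, status unknown. B has change -2 at Week 12 and dies in Week 46. SAP rule at Week 48: A +1, B -1. Protocol rule, last common visit Week 12: A -1, B +1. The sign reverses.
- A leaves at Week 12 and a call records death in Week 20. B dies in Week 46. Literal SAP rule: A is alive, so A +1, B -1. With the recorded death counted: A -1, B +1.

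**2. Lowest score for a subject counted alive.** With N subjects and D scored deaths, it is D - (N - D - 1) = 2D - (N - 1), ties aside. For N = 384 and D = 20, 40, 60, 80 this gives -343, -303, -263, -223. The first death scores -383.

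**3. How many are exposed at Weeks 72 and 96.** SAP 4.2 gives 384 randomised and 202 enrolled in A04. 384 - 202 = 182, or 47.4%. This assumes that enrolment had ended at SAP signing, and the FAS is slightly smaller. If a share r of the 384 have a recorded death before A04 entry, the number scored alive is 182 - 384r:

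| r (assumed) | scored alive | share of the 73,536 pairs involving at least one |
|---|---|---|
| 0 | 182 | 72.4% |
| 10% | 144 | 61.0% |
| 20% | 105 | 47.3% |
| 30% | 67 | 31.9% |

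The pair share is 1 - C(384 - k, 2)/C(384, 2), where k is the number scored alive. A04 subjects cut off by the termination (SAP 5.1, 5.2) come on top.

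**4. Effect on the arm comparison at Week 96.** All inputs are assumed: 192 per arm, identical arms; slopes N(-0.25, 0.12) points per week, residual SD 2; Weibull deaths (shape 1.5, log-hazard 0.7 per SD of slope), 30% dead by Week 96; dropout in Weeks 0-48 calibrated to 182/384 non-entrants; five MAR draws combined by Rubin's rules. With deaths to Week 48 known, about 133 are scored alive, of whom 27 are dead (20-30 for 20-40% mortality). With no death after dropout known, about 145 and 38 (28-45). The second case also describes deaths that are recorded but scored as alive under the literal rule.

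Mean rank shift toward the arm with more non-entry, with ranges over separately programmed runs of this model:

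| between-arm difference in non-entry | deaths to Week 48 counted | deaths after dropout not counted |
|---|---|---|
| 0 | +0.2 | +0.4 |
| 5 points | +1.2 | +2.2 |
| 12 points | +1.3 to +2.5 | +2.4 to +4.5 |
| 20 points | +3.7 to +4.7 | +5.9 to +7.5 |

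The Monte Carlo SE is 0.3 in the first two rows, so the first row is zero. Early, late or slope-related dropout gives at most +8.6. The SE of the rank difference is sqrt((384² - 1)/12) × sqrt(2/192) = 110.9 × 0.102 = 11.3. Rejection at nominal 5% is 2-6%, and 2-8% over all dropout patterns.

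The chance SE of the non-entry difference is sqrt(2 × 0.474 × 0.526/192) = 5.1 points. By chance alone, 12 points has p = 0.019 and 20 points p = 0.0001.

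**5. Alternatives.** Scoring survival over common follow-up and then ALSFRS-R at the latest common visit gave shifts between about -1.0 and +1.3 at Week 96. At Week 48 with all deaths known it was slightly worse than the SAP rule at a 20-point imbalance: -2.7 against -0.7. The protocol's rule taken literally went down to -4.9.

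**6. Week 48.** A simpler assumed model with 10-30% dropout gave about 3-9 unseen deaths among 384. A 10-point dropout imbalance moved the difference in mean CAFS score by about 1 point.

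**The case against.** The strongest reply is that nothing material follows. CAFS is one of six secondary endpoints, with nominal p-values and no fixed order (SAP 9.2.2). No bias arises with equal missingness, and no section reports an imbalance. The shifts stay below one SE, and the larger imbalances would be improbable by chance. In a check with an assumed true effect and equal dropout, power was 89% under both the SAP rule and common-follow-up scoring. All of this stands.

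The exposed number is also an upper bound. The 182 can include A02 completers who declined or failed A04 eligibility and subjects stopped administratively, and the simulation treats them all as deaths or dropouts in Weeks 0-48. Protocol 12.2.2 has deaths investigated from A02 randomisation onward; how fully this was done for A02 dropouts depends on A02 documents not supplied. The hidden text of SAP 9.2.2.1.1 may extend or qualify the rule. These points stand too.

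SAP 9.2 includes all available data regardless of early discontinuation, which suggests that recorded deaths are meant to count. That is the sensible reading, but 8.3.2.2 does not say it, and the two should agree.

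Precedence is settled in SAP section 2, and both documents send deviations to the CSR. The missing section 11 entry is therefore a small documentation gap.

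**Conclusion.** The point holds as a wording and reporting defect with a small effect. SAP 8.3.2.2 literally scores a subject as alive even if a death was recorded after discontinuation, scores unknown vital status as survival, and departs from Protocol 17.4.5.4 without an entry in section 11. The shift is zero with equal missingness. Under the assumed model it is 1 to 9 ranks for imbalances of 5 to 20 points, against an SE of 11-12. The primary analysis does not use the rule.

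Three stronger readings are not supported.
- **That CAFS is materially biased or its error rate inflated.** By-arm missingness is not in the documents, and rejection stays near or below nominal apart from isolated cells at up to 8%.
- **That the main scoring rule should be replaced, or the protocol's restored.** Common-follow-up scoring does better at Week 96 but slightly worse at Week 48 with all deaths known, and the literal protocol rule is biased the other way.
- **That 182 subjects will be scored alive, or that 27-38 of them are dead.** The first figure is a ceiling on non-entrants that applies only if the rule extends to Weeks 72 and 96. The second rests on assumed mortality and dropout.

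**What to change.** 1. In SAP 8.3.2.2, state that every death recorded up to the analysis week, including after discontinuation, is scored as a death at its date. Limit the alive-plus-MAR rule to subjects with no recorded death.
2. Keep that as the main rule, across all subjects. Add a sensitivity analysis that scores each pair on survival over common follow-up and then on ALSFRS-R change at the latest common visit, to show how far the result depends on the alive assumption.
3. Report by arm, at Weeks 24, 48, 72 and 96, the number imputed and the number of unknown vital status.
4. List the departure from Protocol 17.4.5.4 in section 11.

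The cost is a few sentences, one extra scoring routine and one count table. In the sensitivity analysis, pairs that include a dropout are compared on shorter follow-up.

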8.3.2.2.1. ALSAQ-40 - Changes from Baseline

The ALSAQ-40 changes from baseline in MT-1186-A02 to all post baseline visits from MT-1186-A02 until the end of MT-1186-A04 will be calculated for each subject where applicable. The ALSAQ is a patient self-report health status PRO (Patient Reported Outcome). The ALSAQ is specifically used to measure the subjective well-being of patients with ALS. There are 40 items in the long form ALSAQ-40, with 5 discrete scales:

- Physical mobility (10 items)
- Activities of daily living and independence (10 items)
- Eating and drinking (3 items)
- Communication (7 items)
- Emotional reactions (10 items)

Patients are asked to think about the difficulties they may have experienced during the last two weeks (e.g. I have found it difficult to feed myself). Patients are asked to indicate the frequency of each event by selecting one of 5 options (Likert scale):

never/rarely/sometimes/often/always or cannot do at all.

The Investigator (or sub-investigator) will evaluate subjects using the ALSAQ-40 and rater scores will be collected at the time points described in *Table 1: Schedule of Activities*. The evaluation results, together with the dates of evaluation, will be recorded in the eCRF. The ALSAQ-40 total score will be derived as the sum of 40 items.

Mitsubishi Tanabe Pharma America, Inc.

8.3.2.2.2. ALSFRS-R score - Changes from Baseline

Changes in ALSFRS-R score (see definition in 8.3.2.1) from baseline in Study MT-1186-A02 to all post baseline visits from MT-1186-A02 until the end of Study MT-1186-A04 will be calculated for each subject where applicable.

8.3.2.2.3. Time to death, tracheostomy, or permanent assisted mechanical ventilation:

From the day of randomization in MT-1186-A02 through EOT/ET in MT-1186-A04, the Investigator (or subinvestigator) will investigate the presence or absence of the following events:

- Death
- Tracheostomy
- Permanent assisted mechanical ventilation (≥ 23 hours/day)

If any of the events are present, the following will be recorded in the eCRF; the date of the event and EOS date will be recorded. When a subject discontinues the study, study sites must follow-up with phone calls at the time points described in *Table 1: Schedule of Activities*. The evaluation results, together with the dates of the evaluation, will be recorded in the eCRF. The time to first occurrence of death, tracheostomy, or permanent assisted mechanical ventilation (defined on EMA Guideline on clinical investigation of medicinal products for the treatment of amyotrophic lateral sclerosis, 1 November 2015) will be derived as follow:

- o In case the first occurrence from at least one event mentioned above is observed any time up to the last observed visit date when MT-1186-A04 interim data base is locked, then the time variable for each subject will be calculated as:
 - The date of the event Randomization date in Study MT-1186-A02 +1
- o In case none of the events mentioned above are observed until the last observed visit date, a right censoring will be performed for each subject at the last observed date of treatment, the time variable for each subject will be calculated as:
 - Last observed Date Randomization date in Study MT-1186-A02 +1
- o Indicator (censoring) variable will be created to indicate an event (0) if the event was observed or censoring (1) if the event is not observed at interim data base lock and the subjects was either discontinued or is ongoing.

8.3.2.2.4. %Slow Vital Capacity (%SVC) - Change from Baseline

%SVC changes from baseline in Study MT-1186-A02 to all post baseline visits from MT-1186-A02 until the end of Study MT-1186-A04 will be calculated for each subject where applicable. SVC measurements will be conducted in clinic at around the same time of day where possible with the subject in a sitting upright position. Subjects should make at least 3 attempts to generate

Mitsubishi Tanabe Pharma America, Inc.

acceptable and reproducible SVC data. If subjects cannot complete all three attempts due to disease progression or other reasons, it will not be considered a protocol deviation. The best value will be selected and will be recorded in the eCRF.

